1.7 Selective internal radiation therapy (SIRT, radioactive microspheres) for cancer

Selective internal radiation therapy (SIRT) has been used to deliver high dose of radiation to tumor, while minimizing damage to surrounding normal tissues. Various radioactive particles have been used. In this study, we will use Yttrium-90 (^{90}Y -) microspheres (SIR-Spheres®

microspheres).

Due to the size of microsphere (20-60 μ m), yttrium-90 microspheres (SIR-Spheres®) become trapped within arteries supplying liver tumors exposing them to high dose radiation.

Hypervascular hepatic tumors such as hepatocellular carcinoma obtain their blood supply almost exclusively from the hepatic artery whereas normal liver parenchyma receives 75% of its blood supply from the portal vein. There are three times more arterial vessels supplying hepatic tumors than normal liver parenchyma. Therefore, the microspheres lodge preferentially within the vasculature of liver tumors, with minimal amounts lodging in the normal liver parenchyma and, ideally, no amounts distributing to other organs, particularly to the lung.

Over 14,000 people have been treated with SIR-Spheres® microspheres at more than 200 locations in >25 countries across the globe. SIR-Spheres® microspheres are currently being used to treat primary and secondary tumors of the liver such as hepatocellular carcinoma and colorectal, breast and neuroendocrine tumors, respectively. There are significant numbers of reports in the literature supporting the efficacy and safety of the use of yttrium-90 for treatment of such tumors. The largest treating countries are the USA, Australia, Germany, Spain, Italy, New Zealand, and Hong Kong, with treatment experience rapidly growing in other EU countries, Turkey and other countries. Treatment has been predominantly for liver metastases derived from colorectal cancer and other solid tumors in western countries and for hepatocellular carcinoma in the Asian countries and Southern Europe.

1.8 SIRT for metastatic uveal melanoma

Radioactive plaque and proton beam radiation have been used for treatment of primary uveal melanoma. Although melanoma cells are generally resistant to radiation, treatment of metastatic uveal melanoma with high-dose local radiation might have therapeutic benefits. In our institution, a total of 12 uveal melanoma patients, five men and 7 women, ages 48-81 (median 65) with hepatic metastases were treated with SIRT due to tumor progression after trans-arterial embolization (n=9), complications of trans-arterial embolization (n=1) or patient preference (n=2) (32). Patients had both hepatic lobes treated on separate occasions (n=7), one lobe (n=3) or whole liver (n=2) therapy. Treatment dose per patient was reduced by 25% due to prior trans-arterial embolization procedures. The mean total SIRT dose delivered was 1.0 GBq (0.62-1.47 GBq). Five patients had

an increase in hepatic enzymes (Grade1-4) at 1-month follow-up. No procedure related deaths or serious adverse events were experienced. Best tumor response was as follows: CR (n=0), PR (n=0), SD (n=8), PD (n=4), with a median follow-up of 7.8 months (1.0-16.0). The median time to liver progression was 7.0 months (1.0-15.5). Nine of the 12 patients, including 2 patients with >25% pretreatment tumor burden, died due to progression of liver disease (n=6), extrahepatic disease (n=1) or both (n=2). Post-SIRT, median overall patient survival was 10.8 months (1.0-19.0). Three patients (ECOG 0 performance status) are still alive at 13.5-19.0 months (median 16.2 months) following SIRT. Although this is a small retrospective study at a single institution conducted in heavily pre-treated patients, the potential efficacy of radiosphere treatment in metastatic uveal melanoma was suggested. Our observation is supported by a report from other institutions (33) and warrants further investigation in a prospective clinical study. In this clinical trial, we will prospectively investigate the safety and efficacy of SIRT using yttrium-90 SIR-Spheres® microspheres in uveal melanoma patients with hepatic metastases. Patients will be stratified based on their history of previous transarterial embolization of the hepatic artery. The safety and efficacy of treatments will be separately analyzed in these two patient cohorts.

2.0 Study Objectives and Endpoints

2.1 Study Objectives

2.11 Primary Objectives

- (1) Investigate the potential efficacy (clinical response) of radioactive yttrium⁹⁰ microspheres in hepatic metastasis from uveal melanoma.
- (2) Investigate the safety of radioactive yttrium⁹⁰ microsphere in patients with metastatic uveal melanoma.

2.12 Secondary Objectives

- (1) Survivals: Investigate overall survival (OS), progression free survival without progression of hepatic metastasis (PFS-L), and duration of response.
- (2) Correlation between molecular characteristics of metastatic uveal melanoma and treatment outcomes.

2.2 Study Endpoints

- (1) Response Rate: 60% stabilization rate (CR+ PR+SD) warrants future study.

(2) Adverse Events: Treatment-emergent and related serious adverse events, and Grade 3 and 4 laboratory abnormalities for safety assessments.

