3.0 Study Design

This is an open-label, uncontrolled single institution phase II study for metastatic uveal melanoma. Uveal melanoma patients who received one or less prior trans-arterial embolization treatment of hepatic metastasis are eligible. Patients will be stratified into two groups: Group A, no prior intra-hepatic arterial treatment, n=24; Group B, one prior hepatic trans-arterial embolization treatment, n=24. They will be treated with intra-hepatic arterial infusion of Yttrium-90 radioactive microspheres (SIR-Spheres® microspheres).

Within 4 weeks prior to radiosphere treatment, patients undergo the pre-assessment angiogram and technetium-99m-labelled macroaggregated albumin (^{99m}Tc -MAA) nuclear scan to block the collateral flow to non-target organs and to calculate the shunting rate to the lung. Once patients meet the eligibility criteria of the study, the radiosphere treatment will be given. The Yttrium-90 radioactive microsphere treatment generally consists of two sequential uni-lobar treatments, approximately 4 weeks (3 to 5 weeks) apart. In selected patients, if clinically feasible, a biopsy of hepatic metastasis will be obtained prior to radiosphere treatment to investigate the correlation between efficacy of treatments and molecular characteristics of metastatic uveal melanoma.

The side effects of Yttrium-90 radioactive microspheres will be monitored every 2 weeks for one month following each treatment and then every month for three months after the last radiosphere treatment. The efficacy of radiosphere treatment will be evaluated every 3 months from the last treatment for 2 years until disease progression or death.

If patients experience grade 3 toxicity after the first treatment with Yttrium-90 radioactive microspheres, the second radiosphere treatment will be held until the resolution of toxicity to grade 1 or less or for a maximum of 6 weeks. The dose of the second radiosphere treatment will be decreased by 50% for liver-related grade 3 toxicity. A dose reduction will not be considered for

grade 3 GI toxicity unless the next treatment is repeated to the same hepatic lobe. The study treatment will be discontinued for grade 4 toxicity or if patients do not recover from the grade 3 toxicity to at least a grade 1 within 6 weeks.

The study will require two years of accrual with an additional two years of follow-up for survival analysis.

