8.4 Expected Adverse Reactions

Common adverse effects

When the patient is treated with the proper technique, without excessive radiation to any organ, the common adverse events after receiving SIR-Spheres® microspheres are fever, transient decrease in hemoglobin, mild to moderate abnormality of liver function tests – specifically a mild increase in SGOT, alkaline phosphatase and bilirubin, abdominal pain, nausea, vomiting, and diarrhea. The majority of adverse events are grade 1 and 2 toxicity.

Most patients develop a post-operative fever that starts immediately after implantation of SIR-Spheres microspheres® and can last from a few days to a week. The fever does not necessarily indicate sepsis but may be related to the embolic effect of the microspheres and the acute toxic effects on the tumor. If there is any suspicion of bacterial infection, blood culture will be performed and appropriate antibiotics will be given.

Many patients experience nausea that may last up to several weeks and this may occasionally be severe enough to require anti-emetic medication that should be continued until the symptoms subside.

Serious Abdominal Pain

Many patients experience abdominal pain immediately after administration of SIR-Spheres® microspheres and may need pain relief with narcotic analgesia. The pain generally subsides within an hour or so, but patients may require oral analgesia for up to several days.

Immediate, excessive abdominal pain after implantation of SIR-Spheres® microspheres may indicate that microspheres have been inadvertently delivered to other organs such as the pancreas, stomach or duodenum. This will result in acute pancreatitis or peptic or duodenal ulceration. A post-implantation nuclear scan will verify the placement of the microspheres. This is performed with a gamma camera, which will pick up the secondary radiation from the yttrium-90. The introduction of microspheres into the vasculature of the stomach, duodenum or other organs of the gastrointestinal tract can cause chronic pain, ulceration and bleeding. Additional tests such as

serum amylase are also indicated if pancreatitis is suspected. If this were to occur the patient should be treated using best standard practice, including pain relief, and intravenous fluids.

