11.1.3 Adverse Event Reporting Period

The adverse event reporting period for this trial begins when the patient receives the first radiosphere treatment and ends 3 months after the last radiosphere treatment. All adverse events that occur in trial subjects during the adverse event reporting period specified in the protocol will be reported, whether or not the event is considered treatment-related.

In addition, even after the completion of adverse event reporting period, if investigators consider that patients develop a serious adverse event that would be possibly related to the study treatment, such SAE will be reported.

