11.1.4 Seriousness

Each adverse event is to be classified by the investigator as SERIOUS (including life-threatening) or NON-SERIOUS. This classification of the gravity of the event determines the reporting procedures to be followed.

An adverse event that meets one or more of the following criteria/outcomes is classified as SERIOUS:

- Death
- Life-threatening (*i.e.*, immediate risk of death)
- Inpatient hospitalization or prolongation of existing hospitalization
- Persistent or significant disability/incapacity
- Congenital anomaly/birth defect in the offspring of a subject
- An event not included in the list above, but one that jeopardizes the subject or may require intervention to prevent one of the outcome listed above

A NON-SERIOUS event is one that does not meet the criteria described for a serious or life-threatening event.

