12.0 Statistical Considerations

This is a phase II clinical trial to investigate safety and efficacy of radioactive microsphere (*SIR-Spheres® microspheres*). Uveal melanoma patients with progressing hepatic metastases who received no more than one intra-hepatic arterial treatment will be enrolled. Patients will be first stratified into two groups: Group A, no prior intra-hepatic arterial treatment; Group B, one prior intra-hepatic arterial treatment).

A total of 24 uveal melanoma patients will be enrolled into each group. The primary endpoint of this study is the clinical benefit rate (CR+PR+SD). A Simon's two-stage optimal design (alpha=0.05, beta=0.20) will be applied to each group of patients (42, 43). The 60% of clinical benefit rate will be considered effective enough for the future investigation of this treatment. The radiosphere treatment will be considered to be ineffective if clinical benefit rate is 30% or less.

Choice of design is guided by a desire to stop the trial early if the actual stabilization rate is 30% or less. If the stabilization rate is 60% or greater, we would like to have a low probability of failing to conclude effective. Based on the optimal design, we will:

	Look after this number of patients	Stop if number of successes is less than or equal to
Stage I:	8	3
Stage II:	24	10

With this design, we have no more than a 5% chance of concluding effective ($\geq 60\%$ success rate) when the success rate is at most 30%. Similarly, we have no more than a 20% chance of concluding ineffective ($\leq 30\%$ stabilization rate) when it is effective. If the actual response rate is 30% or worse, we have at least a 0.81 probability that the trial will stop after the first 8 subjects. If the response rate is $\geq 60\%$, the probability that the trial will be stopped in stage I is 0.17. The overall power of this design is 80.6%.

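### The Section 2.2 safety endpoint has, on its plain reading, no place for non-serious grade 3 or higher clinical toxicity, and Section 12.0 leaves toxicity undefined

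*Combined protocol and SAP*

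**What the plan says.** Section 2.11 lists as its second primary objective: "Investigate the safety of radioactive yttrium⁹⁰ microsphere in patients with metastatic uveal melanoma". The endpoint that answers it is in Section 2.2 and, in the same words, in the Protocol Summary: "Adverse Events: Treatment-emergent and related serious adverse events, and Grade 3 and 4 laboratory abnormalities for safety assessments".

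Section 11.1.4 classes an event as serious if it meets at least one of six outcome-type criteria, and adds: "A NON-SERIOUS event is one that does not meet the criteria described for a serious or life-threatening event". CTCAE grade is not among the criteria.

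Section 3.0 uses grade to govern the second session: "If patients experience grade 3 toxicity after the first treatment with Yttrium-90 radioactive microspheres, the second radiosphere treatment will be held". The rule is not limited to serious or laboratory events. Clinical toxicity is plainly within its scope, since the next lines deal with dose reduction for "grade 3 GI toxicity unless the next treatment is repeated to the same hepatic lobe".

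Collection is broad. Section 11.1.3 has adverse events reported from the first treatment until 3 months after the last, regardless of relatedness, and Section 11.2 grades their maximum intensity by CTCAE v4.0.

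Section 12.0 names the clinical benefit rate as the primary endpoint. On safety it says only that rates, with toxicity given as an example, will carry confidence intervals. Section 1.8 says that safety will be analysed separately in the two cohorts.

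**The concern.** The endpoint has a serious-event part and a laboratory part. A severe clinical event that is not serious belongs to neither. Such events are plausible here. Section 8.4 expects abdominal pain that may need narcotic analgesia, and nausea that is occasionally severe enough to need anti-emetics. Section 5.4 gives treatment on an outpatient basis with 23-hour observation permitted, so a patient could have grade 3 pain or vomiting without an inpatient stay.

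The protocol treats such an event as important enough to delay the second session and, if it does not resolve in time, to end study treatment. A safety rate built on 2.2 could then omit the toxicity that interrupted treatment. The trial is uncontrolled, so this rate is what a reader will set against other liver-directed treatments.

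A second uncertainty is attribution. The investigators assign it (Section 11.3), and Section 8.4 concedes that radiation hepatitis is hard to diagnose. If the endpoint counts only serious events judged related, it depends on that judgement. The wording does not settle whether it does.

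**Working it through.** **The plan's own figures.** No safety sample size, toxicity threshold or expected toxicity rate is given, so there is no safety figure to reproduce. The design figures in Section 12.0 concern efficacy only. With 8 then 24 patients, and stopping at 3 or fewer and 10 or fewer, the chance of concluding effective is the sum over x = 4 to 8 of P(X1 = x) × P(X2 ≥ 11 − x), where X1 is binomial on 8 patients and X2 on 16. It is 0.806 at a true rate of 60% (stated 80.6%) and 0.046 at 30% (stated no more than 5%). Neither depends on how toxicity is defined.

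**Step 1: which events the endpoint counts.** The serious-event phrase can be parsed in three ways:

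- (a) serious events that are both treatment-emergent and related (the plain reading);
- (b) all treatment-emergent adverse events, plus related serious events;
- (c) treatment-emergent serious events, plus related serious events.

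For events within the reporting period:

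| Event | (a) | (b) | (c) |
|---|---|---|---|
| Related serious event | counted | counted | counted |
| Grade 3 or 4 laboratory abnormality | counted | counted | counted |
| Serious event judged unrelated | not counted | counted | counted |
| Non-serious grade 3 clinical event | not counted | counted | not counted |

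Two of the three readings omit the last row. The third row changes with the reading.

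**Step 2: set this against the rest of the protocol.** The hold rule in 3.0 covers all four rows at grade 3. Sections 11.1.3 and 11.2 collect and grade all four. Section 12.0 reports a toxicity rate without saying which rows it covers. The events are therefore in the data, but no text says that they are in the reported rate.

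**Step 3: which grades.** A life-threatening event is serious under 11.1.4, so grade 4 clinical events of that kind are already covered. In practice the gap is chiefly grade 3.

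**Step 4: possible size.** Let x be the patients counted under reading (a) and m the further patients whose only severe event is non-serious and clinical. In a group of n the rate is too low by m/n. One patient is worth 1/24 = 4.2 percentage points in a full group, and 1/8 = 12.5 points in a group that stops after stage I. The documents give neither x nor m. As an illustration with assumed x = 3, n = 24 and exact (Clopper-Pearson) 95% limits, with lower limit Beta(0.025; k, n − k + 1) and upper limit Beta(0.975; k + 1, n − k) for k = x + m:

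- m = 0: 3/24 = 12.5% (2.7% to 32.4%), no understatement;
- m = 1: 4/24 = 16.7% (4.7% to 37.4%);
- m = 3: 6/24 = 25.0% (9.8% to 46.7%).

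These counts are not forecasts. The intervals overlap heavily, so at this sample size the issue is what the rate describes, not a sharp numerical contrast.

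**The case against.** The strongest reply is that nothing is lost. All adverse events are reported and graded, Section 11.4 sends a summary of them to the DSMB each quarter, and Section 12.0 does not restrict toxicity to serious or laboratory events. A reader might infer from 2.2 that these events never reach any safety result. The documents do not support that, since an analyst could include them under Section 12.0. What remains is that nothing requires it, and the only written definition points the other way.

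A reader might also infer that the primary safety result is biased. Section 12.0 names only the clinical benefit rate as primary endpoint and sets no safety test, so no formal primary safety result exists. The point concerns the endpoint attached to a primary objective.

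Reading (b) has some support. Section 11.1.3 collects all events within the reporting period and only possibly related serious events after it, which resembles that split. It is therefore not established that serious events judged unrelated are excluded. Wording that yields different rates under different readings still needs repair.

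It is tempting to add ulceration and pneumonitis to the missed events. The statement that misplaced microspheres "can cause chronic pain, ulceration and bleeding" describes delivery to the gastrointestinal vasculature, and such complications may often be serious under the non-hospitalisation criteria of 11.1.4. Section 8.4 also says that most events are grade 1 and 2. This objection stands, and it narrows the gap mainly to pain, nausea and vomiting.

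Finally, an endpoint need not mirror a hold rule, and individual records can explain a delayed session. That is true, but a summary rate of severe toxicity should still say whether severe clinical events are in it.

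**Conclusion.** The point holds in limited form. On its plain reading, the endpoint for the safety objective has no category for non-serious grade 3 or higher clinical toxicity. The treatment of serious events judged unrelated is ambiguous, and Section 12.0 leaves toxicity undefined. A severe-toxicity rate reported under 2.2 could be too low.

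The size is unknown. The 12-patient institutional series in Section 1.8 reports no serious adverse events and gives no count of non-serious grade 3 clinical events. The illustrative doubling from 12.5% to 25.0% rests on assumed counts, and with m = 0 there is no understatement at all. No decision rule or efficacy figure is affected.

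The conclusion rests on two assumptions: that both adjectives in 2.2 qualify serious events, and that some grade 3 clinical events will be managed without meeting any seriousness criterion. It says nothing on whether the hold or dose rules are right.

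**What to change.** Put one definition in Section 2.2, the Protocol Summary and Section 12.0: the proportion of treated patients with at least one treatment-emergent CTCAE v4.0 grade 3 or higher adverse event, clinical or laboratory. Report it by cohort with an exact confidence interval. Show the all-cause and treatment-related rates side by side, and serious events as a sub-table.

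Two details belong in the same amendment:

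- Count grade 3 and 4 laboratory abnormalities even when they fall short of the adverse-event definition in 11.1.1, which asks for intervention or further investigation. Otherwise the new rate would lose values that 2.2 now includes.
- Tie treatment-emergent to a stated window. Section 11.1.3 runs to 3 months after the last treatment, whereas the Summary ends safety collection earlier if another treatment for progression starts or the patient dies.

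The cost is one amended definition in three places. The events are already collected and graded, so no new data are needed, and no clinical hold or dose rule changes. The drawback for the sponsor is a possibly less favourable safety rate.

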2.3 Other Parameters

Overall survival (OS), progression free survival (PFS) and duration of response

3.0 Study Design

This is an open-label, uncontrolled single institution phase II study for metastatic uveal melanoma. Uveal melanoma patients who received one or less prior trans-arterial embolization treatment of hepatic metastasis are eligible. Patients will be stratified into two groups: Group A, no prior intra-hepatic arterial treatment, n=24; Group B, one prior hepatic trans-arterial embolization treatment, n=24. They will be treated with intra-hepatic arterial infusion of Yttrium-90 radioactive microspheres (SIR-Spheres® microspheres).

Within 4 weeks prior to radiosphere treatment, patients undergo the pre-assessment angiogram and technetium-99m-labelled macroaggregated albumin (^{99m}Tc -MAA) nuclear scan to block the collateral flow to non-target organs and to calculate the shunting rate to the lung. Once patients meet the eligibility criteria of the study, the radiosphere treatment will be given. The Yttrium-90 radioactive microsphere treatment generally consists of two sequential uni-lobar treatments, approximately 4 weeks (3 to 5 weeks) apart. In selected patients, if clinically feasible, a biopsy of hepatic metastasis will be obtained prior to radiosphere treatment to investigate the correlation between efficacy of treatments and molecular characteristics of metastatic uveal melanoma.

The side effects of Yttrium-90 radioactive microspheres will be monitored every 2 weeks for one month following each treatment and then every month for three months after the last radiosphere treatment. The efficacy of radiosphere treatment will be evaluated every 3 months from the last treatment for 2 years until disease progression or death.

If patients experience grade 3 toxicity after the first treatment with Yttrium-90 radioactive microspheres, the second radiosphere treatment will be held until the resolution of toxicity to grade 1 or less or for a maximum of 6 weeks. The dose of the second radiosphere treatment will be decreased by 50% for liver-related grade 3 toxicity. A dose reduction will not be considered for

grade 3 GI toxicity unless the next treatment is repeated to the same hepatic lobe. The study treatment will be discontinued for grade 4 toxicity or if patients do not recover from the grade 3 toxicity to at least a grade 1 within 6 weeks.

The study will require two years of accrual with an additional two years of follow-up for survival analysis.

